## **II. Study Procedures**

### Inclusion/Exclusion Criteria

Patients will be included if they are having an in-patient spinal fusion procedure, are 18 years or older, post and post-operative pain control plan includes opioid medications. Patients will be excluded if they are pregnant, nursing, under the age of 18, have an allergy to naloxone or its related products, or if they are having an outpatient procedure.

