### Screening procedures

Patients will be screened at the pre-operative clinic visit based on the inclusion and exclusion criteria.

Historical controls will be identified by a report of patients undergoing spinal fusion procedures

identified via ICD9 codes in the previous 3 years. ICD-9 codes include a short fusion surgery (81.06, 81.62) with 3 or fewer vertebral body segments, long fusion surgery (81.63, 81.64), more than 4 vertebral segments, anterior approaches (81.06) and posterior approaches (81.07) in the thoracic and lumbar spine. The historical controls will be matched to active participants based on age, gender, Charleston co-morbidity index, complexity of surgery, and duration of surgery.

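### The two cohorts have no common stated procedure set, and approach and spinal region are neither named matching factors nor covariates, so case mix could bias the primary comparison

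*Combined protocol and SAP*

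**What the plan says.** **Naloxone patients.** Inclusion/Exclusion Criteria states: "Patients will be included if they are having an in-patient spinal fusion procedure". The patient must also be an adult whose "post-operative pain control plan includes opioid medications". No spinal region is specified. Screening procedures adds: "Patients will be screened at the pre-operative clinic visit based on the inclusion and exclusion criteria".

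**Controls.** The same section then uses another route: "Historical controls will be identified by a report of patients undergoing spinal fusion procedures", found by procedure code over the previous 3 years. The code list has three parts:
- The first length class reads "ICD-9 codes include a short fusion surgery (81.06, 81.62) with 3 or fewer vertebral body segments".
- The second length class, which starts above 4, reads "long fusion surgery (81.63, 81.64), more than 4 vertebral segments".
- The part on surgical approach, which alone mentions region, reads "anterior approaches (81.06) and posterior approaches (81.07) in the thoracic and lumbar spine".

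**Matching.** Controls are to be "matched to active participants based on age, gender, Charleston co-morbidity index, complexity of surgery, and duration of surgery". Complexity is not defined.

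**Prognosis.** Background and Significance says that anterior approach and longer surgery raise the incidence of post-operative ileus.

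**Analysis.** The Analysis Plan compares time to first bowel movement by a paired t-test and by a frailty model clustered on matched strata. It names no covariate for either.

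**The concern.** The trial is historically controlled, so matching is the main stated protection against confounding. That protection needs both cohorts to come from the same kinds of operation and the match to cover the features of surgery that affect bowel recovery. On the text, neither is assured.

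One cohort is open to any spinal region, while the other is described, at least in part, as thoracic and lumbar. Of the two surgical risk factors in the Background, duration is matched by name and approach is not. A difference between cohorts that the match does not absorb would pass into both primary analyses. The t-test takes no covariate. A frailty term handles correlation within strata but does not remove a systematic difference between cohorts. The result could be a false naloxone effect or a real one hidden.

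**Working it through.** **Step 1. Set the sections side by side.**

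| Item | Naloxone cohort | Historical controls |
|---|---|---|
| Source | Pre-operative clinic visit | ICD-9 report |
| Region | No limit stated | Thoracic and lumbar, at least for the approach codes |
| Approach | No limit stated | Anterior and posterior codes listed; not a named matching factor |
| Length | No limit stated | Up to 3 segments, or above 4; exactly 4 is in neither class |
| Duration | Matched | Matched |

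Code 81.06 stands under both short fusion and anterior approach. The code groups are therefore not separate classes that could serve as a definition of complexity without further wording.

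**Step 2. Reproduce the plan's power.** Inputs are from Power Analysis: 150 per group, 45% and 30% without a bowel movement at 5 days, hazard ratio (HR) 1.508, two-sided alpha 0.05, stated power 80.1%.
- Events: 150 × (1 − 0.45) + 150 × (1 − 0.30) = 82.5 + 105 = 187.5.
- Schoenfeld power: Φ(√187.5 × ln 1.508 / 2 − 1.96) = Φ(13.693 × 0.2054 − 1.96) = Φ(0.852) = 80.3%.

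The plan's figure reproduces, so this point does not rest on a power error.

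**Step 3. Illustrate the bias.** The documents give no case-mix shares and no effects of region or approach, so both are assumed here. The simulation used 150 per group, exponential times, a control rate of 0.160 per day and censoring at 5 days, with 8,000 runs per cell. Censoring at a second intervention was not simulated, and the main cells ignore existing matching. With no imbalance, the rate of declaring naloxone faster was 2.8% (nominal 2.5%).

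*Region.* Let a share p of naloxone patients come from a region absent among controls, with k times the control rate, and let naloxone be inert. The hazard ratio at time zero is 1 + p(k − 1). For p = 0.2 this is 1.10 (k = 1.5) or 1.20 (k = 2). Over 5 days it averages 1.09 or 1.15, because the faster patients leave the risk set early. Rates of falsely declaring naloxone faster (log-rank):

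| Share p | k = 1.5 | k = 2 |
|---|---|---|
| 2% | 2.8% | 2.9% |
| 5% | 3.7% | 4.4% |
| 10% | 4.4% | 6.8% |
| 20% | 7.9% | 15.6% |
| 30% | 12.3% | 28.7% |

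At p = 20% the paired t-test (hours cut at 120, an assumption) gave 7.0% and 15.5%. A shared gamma frailty model (1,000 runs, error about 1 point) gave 9.6% and 16.7%. If existing matching absorbs half of the log rate difference, the log-rank figures fall to 4.7% and 6.6%.

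*Opposite direction.* If that 20% is slower (0.67 or 0.5 times) and HR 1.508 is true, log-rank power is 60% or 47% instead of 80%.

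*Approach.* Take anterior surgery in 20% of naloxone patients and 40% of controls, at 0.67 or 0.5 times the other rate, with naloxone inert. The hazard ratio is 1.08 or 1.14, and false positives are 6.8% or 11.9%. With the imbalance reversed, the hazard ratio is 0.92 or 0.88. With 28% against 32%, false positives are 3.1% or 3.3%.

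**Step 4. Test the remedy.** In the 20% against 40% example at 0.5 times, the frailty model's null rate was 12.3% unadjusted and 2.6% with approach as a covariate. Adjusted power was 72.0%. With the imbalance reversed, power was 44.1% unadjusted and 76.4% adjusted.

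**The case against.** The other side has several good points.

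- **The region limit may be narrower than it looks.** The thoracic and lumbar phrase may qualify only the approach codes, and the list may not be exhaustive. This stands: the text does not prove that any region is missing among controls. But then the control procedure set is simply not fixed.
- **Complexity may already cover approach and length.** The matching sentence directly follows the code groups, so this reading is plausible. The plan does not say so, and the groups overlap and leave out 4 segments.
- **Duration is matched.** This deals with one of the two named risk factors and may absorb part of the effect of the other. The main illustrations give no credit for it.
- **Ileus is not the primary outcome.** The Background links approach to ileus incidence, not directly to time to first bowel movement.
- **Covariates may be intended.** The Analysis Plan checks proportional hazards for its predictors in the plural. None is named.

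Two stronger readings are tempting and are not supported. A reader might infer that controls are exempt from the eligibility criteria and may include opioid-free patients. However, the criteria speak of patients generally, and Study Design describes the trial population as receiving opioids. What is missing is an express rule for controls. Opioid-free controls with faster recovery (1.5 to 2.5 times, assumed) would work against naloxone, and at 1% to 2% of controls log-rank power would still be 77% to 80%.

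A reader might also infer that the matching lists contradict each other, because the Analysis Plan's list omits complexity. That list explains the random intercepts in the secondary models. The matching itself is set in Screening procedures.

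**Conclusion.** The point holds as a gap in design. Followed as written, the plan allows the cohorts to differ in spinal region and approach, and neither primary analysis is set up to correct for this. The bias could go either way.

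Its size is unknown. The 8% to 16% false-positive range needs a 20% share in a region wholly absent among controls, an assumed rate ratio of 1.5 to 2, and no help from existing matching. With half absorbed it is about 5% to 7%, and with a 2% share it cannot be told from the simulated null. The documents do not support a claim that the trial will favour naloxone, or that the bias is large. Confidence is medium. The correction is cheap and should be made, preferably before controls are drawn.

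**What to change.** 1. State the same spinal regions and procedure set for both cohorts.
2. Define complexity of surgery as approach plus number of segments, in contiguous bands that place a 4-segment fusion, and match on it.
3. Put approach and region in the primary frailty model as covariates wherever they are not exactly matched. Treat that adjusted model as the protected analysis, because the paired t-test cannot adjust.
4. Apply the eligibility criteria to controls in the same form as to naloxone patients: a post-operative pain plan or order that includes opioids. Do not require actual post-operative opioid use in controls. That would be a stricter rule for one cohort only, and it is measured after the start-of-surgery time origin.

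**Cost.** Protocol and SAP wording, a re-run of the control report and some chart checks. A few cases may find no control, and the pool size is not stated. At the planned rates, losing 10% of pairs leaves 135, with 187.5 × 0.9 = 168.75 events and power Φ(12.990 × 0.2054 − 1.96) = 76%. Losing 20% leaves 120, with 150 events and power Φ(12.247 × 0.2054 − 1.96) = 71%. Covariate adjustment instead of exact matching limits this loss of pairs.

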### Study recruitment

Recruitment will take place prior to surgery. Initial contact with prospective participants will occur in the pre-operative clinic visit which occurs 1 – 12 weeks prior to surgery. A member of the study team will provide the patient with a copy of the informed consent document to review and take home. The patient will be given an opportunity to ask any questions they may have about the study. Patients will then be approached on the day of surgery to sign the consent form when surgical consent is obtained. Consent will be obtained by one of the neurosurgery residents involved with the study.

### Screening procedures

Patients will be screened at the pre-operative clinic visit based on the inclusion and exclusion criteria.

Historical controls will be identified by a report of patients undergoing spinal fusion procedures

identified via ICD9 codes in the previous 3 years. ICD-9 codes include a short fusion surgery (81.06, 81.62) with 3 or fewer vertebral body segments, long fusion surgery (81.63, 81.64), more than 4 vertebral segments, anterior approaches (81.06) and posterior approaches (81.07) in the thoracic and lumbar spine. The historical controls will be matched to active participants based on age, gender, Charleston co-morbidity index, complexity of surgery, and duration of surgery.

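### Naloxone patients can enter only through a pre-operative clinic visit 1–12 weeks before surgery, but historical controls come from a procedure-code report with no matching restriction, which may bias the primary comparison

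*Combined protocol and SAP*

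**What the plan says.** **Naloxone group.** Study recruitment states: "Initial contact with prospective participants will occur in the pre-operative clinic visit which occurs 1 – 12 weeks prior to surgery". Screening procedures puts screening at the same point: "Patients will be screened at the pre-operative clinic visit based on the inclusion and exclusion criteria". Consent follows later: "Patients will then be approached on the day of surgery to sign the consent form when surgical consent is obtained". No other way into the group is described.

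**Controls.** Screening procedures states: "Historical controls will be identified by a report of patients undergoing spinal fusion procedures", "identified via ICD9 codes in the previous 3 years". The codes are described by length of fusion, approach and spinal region (thoracic and lumbar). Controls are then "matched to active participants based on age, gender, Charleston co-morbidity index, complexity of surgery, and duration of surgery".

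**Eligibility.** Inclusion/Exclusion Criteria begins: "Patients will be included if they are having an in-patient spinal fusion procedure, are 18 years or older". It also requires a post-operative pain plan that includes opioids. The exclusions are pregnancy, nursing, age under 18, naloxone allergy and outpatient surgery. Urgency and indication are not mentioned.

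**Analysis.** The Analysis Plan gives two approaches to the primary aim: a paired t-test (or Wilcoxon signed-rank test), and a frailty survival model clustered on matched strata. Neither names a covariate for urgency or indication.

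**The concern.** The study is not randomised, so comparability rests on how controls are chosen. Someone fused at short notice, for example after trauma or transfer, would normally have had no clinic visit at least a week earlier and could not be recruited as the text stands. The same patient in the previous 3 years would appear in a report built on fusion codes unless some unstated step removed them.

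Such patients may differ in mobility, neurological state and opioid use before surgery. If they are slower to a first bowel movement and are present only among controls, the naloxone group looks faster even when the drug does nothing. Ileus, constipation, opioid requirement and length of stay could be affected in the same way. The Power Analysis attributes the whole hazard ratio of 1.508 to naloxone and makes no allowance for a baseline difference.

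**Working it through.** **1. Can any step in the plan close the gap?**

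- *Eligibility criteria.* An adult in-patient with an urgent fusion and opioid orders can satisfy every inclusion criterion and meet no exclusion. Applying these criteria to controls would leave that patient in. The restriction to scheduled patients comes from the recruitment route, which has no counterpart for controls.
- *Matching.* The factors are age, gender, a co-morbidity index, complexity and duration of surgery. Urgency and indication are not named.
- *Models.* Pairing and frailty account for correlation within matched strata. They do not adjust for a factor that differs systematically between the groups within strata.

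**2. The plan's own power figure.** Inputs are from the Power Analysis: 45% and 30% without a bowel movement at 5 days, 150 per group, two-sided alpha 0.05.

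- Rates: −ln(0.45)/5 = 0.160 and −ln(0.30)/5 = 0.241 per day.
- Hazard ratio from the unrounded rates: 0.2408/0.1597 = 1.508.
- Expected events: 150 × 0.55 + 150 × 0.70 = 187.5.
- Schoenfeld power: Φ(√187.5 × ln 1.508 / 2 − 1.96) = Φ(2.81 − 1.96) = 80.3%, against the stated 80.1%.

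The power figure reproduces, so there is no arithmetic error here.

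**3. Illustration of size under no drug effect.** The documents give neither the share q of urgent patients among matched controls nor their rate ratio r against scheduled patients, so both are assumed. The plan's control rate of 0.160 per day is used as the scheduled-surgery rate in both groups. Times are exponential, with 150 per group and censoring at 5 days.

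The expected proportion of controls without a bowel movement at 5 days is (1 − q)·exp(−0.160 × 5) + q·exp(−0.160 × r × 5). For r = 0.5 and q = 30% this is 0.7 × 0.449 + 0.3 × 0.670 = 0.516, against 0.449 with no urgent patients.

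The apparent hazard ratio and rejection rate come from a simulated unstratified log-rank test, 20,000 runs per row. With no urgent controls the simulation rejects 5.0% of the time under no effect, and has 80.1% power at a hazard ratio of 1.508.

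| r | q | Controls with no BM at 5 days | Apparent HR | Two-sided rejection |
|---|---|---|---|---|
| 0.5 | 10% | 47% | 1.06 | 7% |
| 0.5 | 20% | 49% | 1.13 | 12% |
| 0.5 | 30% | 52% | 1.21 | 21% |
| 0.5 | 40% | 54% | 1.28 | 34% |
| 0.7 | 10% | 46% | 1.03 | 6% |
| 0.7 | 20% | 47% | 1.07 | 7% |
| 0.7 | 30% | 49% | 1.11 | 10% |
| 0.7 | 40% | 50% | 1.15 | 14% |

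If urgent patients were faster (r = 1.25, q = 30%), the apparent hazard ratio would be about 0.93, against naloxone.

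**The case against.** The strongest reply is that the documents never mention urgent or trauma fusion. A reader might infer that the report does contain such cases. The text supports only that nothing stated would keep them out. The codes are also confined to the thoracic and lumbar spine, which narrows the pool. Complexity of surgery is undefined and might capture part of what distinguishes urgent cases, and matching on it and on co-morbidity and duration may remove some of the difference. All of this stands. It limits the likely size but does not supply the missing restriction.

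A reader might also infer that the comparison is certainly biased towards naloxone. No section reports time to first bowel movement by urgency, so slower recovery in urgent patients is plausible but not shown.

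A third tempting reading is that controls include people unable to consent for themselves while the naloxone group cannot. Study recruitment does have the patient sign, but the consent pages are not in the public document, so a surrogate route cannot be ruled out. The point does not need this argument.

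Finally, the illustration uses an unstratified log-rank test, not the planned paired or frailty analyses, and its shares are those left after matching, not those in the raw report. At a 10% share the rejection rate is close to nominal, and even the most extreme row stays well below 1.508. Those limits are accepted.

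**Conclusion.** The point holds as a risk of bias, with medium confidence. The two groups enter by different routes, and no stated criterion, matching factor or model term makes them comparable on scheduled versus unscheduled surgery. This is more than missing detail, because following the text exactly can produce groups that differ on this factor.

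The direction is probably towards naloxone, on the assumption that urgent patients have a later first bowel movement. The size depends entirely on the assumed share and rate ratio. Over the slower-recovery scenarios shown it runs from almost nothing (hazard ratio 1.03, rejection 6%) to a spurious hazard ratio of 1.28 with rejection about one time in three. These are illustrations and not estimates for this hospital. The documents do not support a claim that the bias is present, or that it could account for the whole planned effect.

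**What to change.** Add to Screening procedures: *Historical controls must have had a pre-operative clinic visit 1–12 weeks before a scheduled in-patient fusion; urgent, emergency, trauma and transfer admissions are excluded.* Apply this from existing records (clinic-visit date and admission type) before matching.

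Restriction before matching is preferable to a model term, because the paired t-test takes no covariates and the naloxone group should contain no urgent patients from whom to estimate an adjusted contrast. Adding admission type to the matching factors would have much the same effect.

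The cost is one sentence and one extra filter on records already being searched, with no new patients or procedures. The downside is a smaller pool from which to find 150 controls, so some matches may be looser. If the report holds few urgent cases, little is lost.

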### **I. Study Design**

This is a prospective, historically controlled observational trial of enteral naloxone use in patients admitted for spinal fusion surgery and receiving opioids for pain management.

Primary outcome: Time to first bowel movement (hours)

Secondary outcomes:

- Hospital length of stay
- Incidence of post-operative ileus. Post-operative ileus will be diagnosed through a combination of clinical exam and radiographic (X-ray) findings
- incidence of post-operative constipation (defined as 3 days without a bowel movement)
- average numerical pain scale (Adult Nonverbal Pain scale or Visual Analog Scale) on post-operative days 0, 1, 2, and 3
- average daily opioid requirement on post-operative days 0, 1, 2 and 3 (morphine equivalents)
- number of naloxone doses administered
- average number of daily bowel movements,
- number of medication escalations required (defined as use of an as needed laxative medication or addition of a new order for a laxative medication)
- Incidence of adverse effects
- Incidence of study drug discontinuation

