### Study Intervention

Active study agents: Naloxone

Blinding/labeling/preparation of agents: No blinding is required in this study. The study drug will be prepared, unit dose labelled, and patient labelled according to institutional protocols.

Storage: Secured at room temperature in the central pharmacy then dispensed as a patient specific supply and stored at room temperature the automated dispensing cabinet. No more than a 24 hour supply will be dispensed at any given time.

Administration: 4 mg of a 1 mg/ml oral solution administered enterally (oral, nasogastric, orogastric, gastrostomy, or jejunostomy) every 8 hours for 48 hours

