**I. Analysis Plan**

Power Analysis

Power estimates for this study were based on prior work by Lee et al. In their study, patients were randomly assigned to receive morphine with naloxone or morphine without naloxone. They found that those who received naloxone had a shorter time to first postoperative passage of flatus ( $M = 51.9$ hr,  $SD = 16.6$ hr) versus control ( $M = 87.0$ hr,  $SD = 19.5$ hr). Similarly, the authors found that time to first feces was faster in the naloxone cohort ( $M = 95.3$ hr,  $SD = 25.0$ hr) than control group ( $M = 132.9$ hr,  $SD = 29.4$ hr). However, their study duration was exceedingly long with a maximum duration of approximately 160-180 hours. One goal of this study is to estimate the effect of naloxone on time to first feces within the first 120 hours (5 days) following treatment. In this study, patients who require a second intervention or who do not experience flatus or feces by Day 5 will be censored.

The null hypothesis is that the bowel movement (BM) rate is identical in the two groups (control and naloxone). Power is computed to reject this null hypothesis. Computation of power is based on a hazard ratio of 1.508. Specifically, it assumes instantaneous BM rates of 0.160 for the control group versus 0.241 for the naloxone group. This is equivalent to a median time of no BM of 4.34 days for the control group versus 2.879 days for the naloxone group. At 5 days, it is hypothesized that 45% of the control cohort versus 30% of the naloxone cohort will require a second intervention because they have not experienced a BM.

With a total of 150 patients entered into the naloxone group and a total of 150 historical controls, the study will have power of 80.1% to yield a statistically significant result. The

criterion for significance (alpha) is set at 0.050, and the test will be 2-tailed meaning an effect in either direction will be interpreted.

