#### Analysis Plan

Two different approaches will be used for the primary aim. First, a paired *t*-test will be used to estimate the mean difference in hours to first feces between the active cohort and historical control cohort. For this analysis, the origin of time for both groups is start of surgery. If necessary, a Wilcoxon signed ranks test will be used to compare the two distributions.

A second approach will compare the instantaneous rates of bowel movements between the active and control cohorts using a Frailty survival model that allows for clustering of patients within their matched strata. In this analysis, control patients who required treatment for ileus will be censored at the time of such treatment, and active patients who require an additional treatment beyond receipt of naloxone will be censored at the time of such treatment. All patients who do not achieve BM by 120 hours will also be censored. Hours to first feces for both groups will be start of surgery. While we assume there is no immortal time bias between start of surgery and receipt of naloxone for the active cohort, a conditional landmark method may be used to account for the amount of hours between surgery and receipt of naloxone. The proportional hazards assumption for all predictors will be tested using Martingale residuals as described by Lin, Wei, and Ying.

Regarding the secondary aims, a linear mixed effects model will be used to compare LOS between the two groups. A generalized linear mixed effects model will be used to compare the two groups on all other secondary outcomes. In these models, random intercepts will be allowed for each case-control matched strata in order to account for the correlation between cases and controls based on age, gender, Charleston co-morbidity index, and operation time under anesthesia.

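### Historical controls are matched from admissions whose bowel outcome is already recorded, with no matching algorithm or outcome masking, so the primary comparison is open to outcome-aware selection

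*Combined protocol and SAP*

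**What the plan says.** Screening procedures takes the controls from a report of spinal fusion patients "identified via ICD9 codes in the previous 3 years". It then states: "The historical controls will be matched to active participants" on five factors, namely gender, age, a comorbidity index, and the complexity and duration of the operation. That is the whole matching rule. The plan does not give a distance measure, caliper, matching order or tie rule, and it does not say who matches, when, or with which data in view.

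The Analysis Plan describes the matched strata again, as the "correlation between cases and controls based on age, gender, Charleston co-morbidity index, and operation time under anesthesia". This list has four factors: complexity of surgery is missing, and duration of surgery has become time under anaesthesia.

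Both approaches to the primary aim use the matched controls. In the first, "a paired *t*-test will be used to estimate the mean difference in hours to first feces between the active cohort and historical control cohort", with a signed-rank test as fallback. The second is a frailty survival model on the matched strata, censored at 120 hours. The Power Analysis plans for 150 naloxone patients and 150 historical controls.

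**The concern.** In a historically controlled study, choosing the control set takes the place of allocation. If more than one past admission fits an active patient, someone or something must decide which is used. At that moment the candidates' BM times, lengths of stay and ileus diagnoses are already recorded. Duration of surgery is known only after the active patient's operation, so matching cannot be finished before then and may come after that patient's own outcome is known.

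A matcher could follow the text to the letter and still choose with the outcome in view. If slower controls were preferred, even without intent, the comparison would move in favour of naloxone. The frailty term, the optional landmark analysis and the random intercepts would not remove this, because they all take the selected controls as given.

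**Working it through.** **The plan's own figure.** From the Power Analysis: 45% of controls and 30% of naloxone patients without a BM at 5 days, hazard ratio (HR) 1.508, two-sided alpha 0.05, stated power 80.1%.

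- Expected events: 150 × 0.55 + 150 × 0.70 = 82.5 + 105 = 187.5.
- Schoenfeld: z = √187.5 × ln(1.508)/2 − 1.96 = 0.85, power 80.3%.
- Freedman: z = √187.5 × 0.508/2.508 − 1.96 = 0.81, power 79.2%.

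The stated power reproduces and is not at fault. It presumes that controls are chosen independently of their outcome.

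**Is the match fixed by the text?**

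- Complexity of surgery is a matching factor under Screening procedures and absent from the Analysis Plan.
- Short fusion is three segments or fewer and long fusion is more than four, so four-segment fusions have no class.
- Code 81.06 is listed both as a short fusion and as an anterior approach.

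Two people following the text could therefore build different control sets.

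**Size if the choice followed the outcome.** Assumptions, none of them in the documents: no drug effect, two eligible charts per active patient, and the slower chart taken in a share q of pairs, otherwise a random one. From the plan: control rate λ = 0.160 per day, censoring at 5 days, 150 per group. For the t-test, times beyond 5 days are set to 5 days (a further assumption).

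- One random chart: share without BM at 5 days e^(−0.8) = 0.449; mean time up to 5 days (1 − 0.449)/0.160 = 3.442 days.
- Slower of two: share without BM 2 × 0.449 − e^(−1.6) = 0.697; mean time 2 × 3.442 − (1 − e^(−1.6))/0.320 = 4.389 days.
- Difference in mean time: 0.948 days = 22.7 hours, so the mean paired difference is 22.7 × q hours.
- Apparent HR = 0.160 ÷ [(1 − 0.449 − 0.247q)/(3.442 + 0.948q)].

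For q = 0.20 the control rate becomes 0.501/3.631 = 0.138 per day, and HR = 0.160/0.138 = 1.16. False-positive rates come from 10,000 simulated trials per row.

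| Slower chart taken in | Apparent HR | Mean paired difference (hours) | False positives, log-rank | False positives, paired t |
|---|---|---|---|---|
| 0% of pairs | 1.00 | 0 | 5% | 5% |
| 10% | 1.08 | 2.3 | 8% | 8% |
| 20% | 1.16 | 4.5 | 15% | 15% |
| 30% | 1.25 | 6.8 | 29% | 31% |

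Separate simulations put the first non-zero HR at 1.07 to 1.08 and the last false-positive rate at 28% to 31%. The log-rank test stands in for the frailty model.

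**The case against.** The strongest reply is that this is silence, not a stated flaw. The matching factors include no outcome, the source is a report, and the text is equally compatible with an electronic match that never touches bowel records. That stands: the documents do not show that anyone will look.

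The illustration is also hypothetical. The size of the control pool is not given, and five factors at one center may leave few ties. The slower chart would have to be preferred without offsetting choices of the faster one. At 10% of pairs the false-positive rate rises only from 5% to about 8%; the 30% row needs far more than a slight preference. This also stands, and it is why the figures are a range under stated assumptions.

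Three stronger readings are tempting, and the documents do not support them.

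- *The controls will be picked for slow bowel function.* The documents support only that outcomes are already recorded and not withheld. Selection could go either way; slower controls is merely the direction that favours naloxone.
- *The plan waives masking of control selection.* The sentence "No blinding is required in this study" stands under Study Intervention, next to labelling and preparation of the drug. It describes an open-label product and says nothing about matching or chart abstraction.
- *Such a bias could never be found or undone.* The report can be rerun, selected and unselected eligible patients compared, and the match repeated by algorithm. The plan does not call for such a check, and analysis of the chosen 150 alone would not reveal the problem.

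What remains is that the step which decides the comparator is unprotected, and that protection is cheap.

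**Conclusion.** The point holds as an open risk to the primary comparison. The matching procedure is not fixed, outcomes are available when it is carried out, and neither primary analysis can correct for a choice that depended on them. If the slower of two eligible charts were taken in 10% to 30% of pairs, an inert drug would show an HR of about 1.08 to 1.25 and a mean gain of about 2 to 7 hours, with a false-positive rate of about 8% to 30% in place of 5%. Those sizes rest wholly on the two-chart and share-of-pairs assumptions. They show how sensitive the comparison is, and are not an estimate of bias in this trial. The change should be made, because it alters how the study is run and not only how it is described.

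**What to change.** 1. Define the complexity classes so that every fusion falls into exactly one: assign four-segment fusions and resolve the double use of code 81.06. Make the matching lists in Screening procedures and the Analysis Plan agree, including whether the time factor is duration of surgery or time under anaesthesia.
2. Match with a locked script on a file that holds only identifiers and the matching factors. State in advance which factors are matched exactly (for example gender and complexity class), the calipers for the others, the matching order, and a seeded random tie-break.
3. Freeze the matched list before any BM time, length of stay or ileus status is abstracted. Then abstract outcomes for both cohorts from the same charted fields under one rule.
4. Keep the full candidate report, so that selected and unselected eligible controls can be compared.

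Cost: a short script and a set order for pulling chart data. If the comorbidity index or duration of surgery cannot be extracted electronically for the whole pool, someone must abstract them from charts that also hold the outcomes; that adds work and should not be done by the person who matches. A few active patients may have no control inside the calipers. Each lost pair removes about 187.5/150 = 1.25 expected events. If ten pairs were lost (an assumption), 175 events would remain and power would be about 78%, so the calipers should be chosen with this in mind.
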